participant group assignment, as feasible. 2) PN training. Training is addressed in Section B.6 above. 3) Intervention delivery. To ensure consistency of intervention delivery, evaluation of intervention processes is essential and several strategies will be used. DVDs or instructions with a link to view the program on the web will be mailed to participants. All PN calls will be recorded for quality assurance purposes, with a subsample randomly selected for evaluation. Audiotaped PN calls will be evaluated using a checklist we developed in prior studies. Project staff will discuss intervention delivery issues, technical support requests, and any unusual events during biweekly research team meetings. Modifications will be made as necessary and recorded to ensure appropriate intervention delivery and maintenance of protocol integrity. Decisions about modifications will be made jointly by the research team and recorded. 4) Intervention receipt. Since all participants in the intervention arms will receive the tailored DVD via mail or a web link, we will call each participant approximately 2 weeks after mailing to conduct a process evaluation of this intervention. Through the process interview, we will assess receipt of the DVD or web link, how much of the DVD was viewed (none, part, or all), as well as satisfaction with and relevance of the content for those assigned to both intervention groups. Participants will receive a \$50 gift card for completing this process interview. Specific evaluation questions that assess user experience and satisfaction are included elsewhere. 5) Intervention enactment. All participants who return a completed FIT will have enacted the behaviors recommended in the interventions. Those who attend a colonoscopy appointment are routinely asked about their experience with, and ability to complete the bowel preparation and refrain from eating solid food before the test. This information is documented in the EMR, and colonoscopy procedure notes will provide evidence that participants who choose this test have enacted the behaviors recommended in the interventions. **The PN documentation record will provide additional data to support intervention enactment by participants assigned to this group.**

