**C.8. Data Collection. (RQ-6, PC-2, PC-3)** Trained data collectors/interviewers who are employed by the Indiana University Center for Survey Research (CSR) will collect data via structured telephone interviews. Interviews will be conducted at baseline (T1), at 6 months post-baseline (T2), and at 9 months post-baseline (T3). If unable to reach participants when a phone interview is due, we will mail a letter to them requesting that they contact the CSR data collection team so that the interview may be completed. Reminder letters will be mailed to participants about 1 month before the T2 and T3 interviews are due. Process interviews will be conducted with participants assigned to the DVD intervention group approximately two weeks after mailing of the DVD. The baseline interview includes a question to confirm age eligibility and assesses the following: demographics, health literacy, health status, patient activation, CRC knowledge, CRC fear, cancer fatalism, colonoscopy-related procedural anxiety, social support, and media exposure. For both colonoscopy and FIT, the baseline interview asks questions about participants' experience with each test and readiness to screen by each test. Health beliefs for perceived CRC risk and colonoscopy and FIT perceived benefits, perceived barriers, and perceived self-efficacy are also collected. At completion of the baseline interview, participants will be randomized. People assigned to DVD or DVD + PN intervention groups will be told they will receive a DVD or instructions to access the website to view the program (based on their preference). Those in the tailored DVD + PN group will also be told they also will receive a phone call from the nurse navigator in about a week.

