The DVD process interview will assess receipt of, viewing of, and satisfaction with the DVD and will be done approximately 2 weeks post-mailing of the DVD. Receipt, experience and satisfaction with the PN intervention, for those randomized to the DVD+PN group, will be assessed as part of the 6 month interview (T2). The 6 month interview will also assess changes in knowledge, patient activation, CRC fear, cancer fatalism, and colonoscopy-related procedural anxiety. Health beliefs for colonoscopy and FIT will be assessed as will self-reported CRC screening intention, uptake and satisfaction with the screening experience (for those who completed screening). At 9 months, we will assess self-reported CRC screening intention, uptake and satisfaction with the screening experience (for those who completed screening since T2). Participants will receive a \$50 gift card for the baseline interview, a \$50 gift card for the 6 month interview and a \$50 gift for completing the 9 month interview; a total of \$150 for participants who complete all three interviews. Participants who complete the additional DVD process interview will receive another \$50 gift card for a total of \$200 in gift cards. By using gift cards with an appealing dollar amount over the 9 month data collection period, we hope to incentivize participants to remain in the study. Additional retention strategies which we will use include mailing

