**J. Intervention Fidelity.** Published recommendations to ensure intervention fidelity address five components that are described in this section. 1) Study design. The three group design ensures blinding of outcome data collectors to participant group assignment. 2) PN training. Training is addressed in section B.7 above. 3) Intervention delivery. To ensure consistency of intervention delivery, evaluation of intervention processes is essential and several strategies will be used. DVDs or instructions with link to view the tailored DVD on the web will be delivered via an express mailing courier with delivery confirmation. All PN calls will be recorded for quality assurance purposes, with a subsample randomly selected for evaluation. Audiotaped PN calls will be evaluated using a checklist we developed in prior studies. Project staff will discuss intervention delivery issues, technical support requests, and any unusual events during biweekly research team meetings. Modifications will be made as necessary and recorded to ensure appropriate intervention delivery and maintenance of protocol integrity. Decisions about modifications will be made jointly by the research team and recorded. 4) Intervention receipt. Since all participants in the intervention arms will receive the tailored DVD via mail or a web link, we will call each participant approximately 2 weeks after mailing to conduct a process evaluation of this intervention. Through the process interview, we will assess receipt of the DVD or web link, how much of the DVD was viewed (all, part or none), as well as satisfaction with and relevance of the content. Participants will receive a \$50 gift card for completing this process interview. 5) Intervention enactment. All participants who return a completed FIT will have enacted the behavior recommended in the interventions. Those who attend a colonoscopy appointment are routinely asked about their experience with, and ability to complete, the bowel preparation and refrain from eating solid food before the test. This information is documented in the EMR and colonoscopy procedure notes and will provide evidence that participants enacted the behaviors recommended in the DVD. The PN documentation record also will provide data to support intervention enactment by participants assigned to this group.

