- 2) The second group of research staff includes experienced interviewers/data collectors employed by the Center for Survey Research (CSR) at Indiana University. Prior to the study-specific training described below, CSR interviewers/data collectors will have completed a rigorous 9-hour telephone interviewing training course, with four hours spent in hands-on practical experience in which the trainee-to-supervisor ratio is 5:1. This training course covers: 1) the interviewer's role in survey research; 2) standardized interviewing techniques; 3) administration of survey introductions and refusal aversion techniques; 4) use of computerized sample management and data collection systems; 5) protection of human subjects and sensitive information; and 6) daily case management. Comprehension of concepts and techniques and skill in their execution are assessed through a battery of tests at appropriate intervals in the training course; trainees do not matriculate to the next phase until all prior phases are mastered. CSR interviewers/data collectors will then be trained on: 1) administering the study's four phone interviews: T1 (baseline), DVD Process, T2 (6 month) and T3 (9 month); 2) handling problems or questions that arise during data collection; 3) recognizing and reporting potential adverse events; and 4) data monitoring and quality assurance procedures. Training will include demonstrations of effective data collection interviews using the computer-assisted telephone interview software (CATI). Following demonstrations and practice sessions, interviewers/data collectors will role-play and receive feedback until they have reached 100% compliance with guidelines for interviewer data collection integrity.

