### 3) Data Collection

Outcome data collection will be handled by expert interviewers/data collectors at the CSR. A centralized data entry system will be developed and housed on the secure server managed by the CSR. All computers that will be used to collect and send data during implementation of the study or to store data at the central location will be password-protected and backed up nightly. Job performance of the interviewers/data collectors will be closely monitored by the Project Manager and the CSR supervisors to ensure their adherence to the study protocol. Telephone interviewing stations at the CSR allow supervisors to listen to interviews and view computer screens remotely in real-time without the knowledge of the interviewers/data collectors. All interviewers/data collectors will be monitored regularly, with a goal of once during every shift. One monitoring session will include listening to at least 20 interview questions. Ten percent of all interview calls will be monitored for quality assurance purposes. Feedback will be provided after monitoring sessions to correct any performance weaknesses.

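### Having three groups does not blind interviewers: the T2 interview reveals the DVD+PN arm, so blinding of the self-report outcomes is not assured

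*Combined protocol and SAP*

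**What the plan says.** The blinding statement appears twice. Section J of the human-subjects part gives it without qualification: "The three group design ensures blinding of outcome data collectors to participant group assignment". Section C.7 gives the same sentence but ends it "participant group assignment, as feasible". Neither place names a mechanism.

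The plan describes outcome collection as follows.

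- **Who collects.** Project Monitoring, item 3: "Outcome data collection will be handled by expert interviewers/data collectors at the CSR". CSR is the Center for Survey Research.
- **Which interviews they run.** Research Staff Training says this group is trained in "administering the study's four phone interviews: T1 (baseline), DVD Process, T2 (6 month) and T3 (9 month").
- **Process interview.** C.8: "Process interviews will be conducted with participants assigned to the DVD intervention group approximately two weeks after mailing of the DVD". C.7 makes clear that both intervention arms are covered.
- **Navigator items.** C.8 says that receipt of, experience with and satisfaction with navigation, "for those randomized to the DVD+PN group, will be assessed as part of the 6 month interview (T2").
- **Other T2 content.** C.8: "The 6 month interview will also assess changes in knowledge, patient activation, CRC fear, cancer fatalism, and colonoscopy-related procedural anxiety". Health beliefs, self-reported screening and satisfaction with screening are collected in the same call.
- **Participants' knowledge.** C.8: "People assigned to DVD or DVD + PN intervention groups will be told they will receive a DVD". This happens once the baseline interview ends.

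Screening completion, by contrast, is taken from the medical record (C.9).

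**The concern.** Blinding of assessors comes from what assessors can see and hear, not from how many arms are randomised. Here the T2 instrument differs by arm. When the navigator items come up, the interviewer knows that the participant is in DVD+PN, and the outcome and belief questions belong to the same call.

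The measures at stake are answers spoken to an interviewer. Anxiety and satisfaction are tested under H1.3, and the opening of C.9 lists them among the primary study outcomes. Changes in knowledge and health beliefs are the Aim 3 mediators. A reader who relies on section J would take all of these as collected blind, which the procedures do not guarantee.

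Record abstraction raises a smaller, related point. The plan does not say who abstracts screening dates and bowel-preparation ratings, or whether that person can see the arm.

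**Working it through.** The plan gives no figure for blinding, so there is none to reproduce. The check sets the passages side by side and counts the participants affected.

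**Step 1: can the design feature produce the stated property?** No. Three arms and two arms are alike in this respect. Blinding would need, for example, an identical instrument in all arms, separate staff for arm-specific questions, or a rule that those questions come last. The documents describe none of these, and no check of whether blinding held.

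**Step 2: who is revealed at T2?** Navigator items go to DVD+PN only. C.9 describes them as 19 + 20 = 39 satisfaction items, so the module is hard to miss.
- Randomised to DVD+PN (C.12): 150 of 450, or 33%.
- Expected at follow-up: 150 × (1 − 0.25) = 112.5. The plan works with 115, using attrition of about 25%, which E.1 reports at the 6-month time point.

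So about 115 T2 calls contain the revealing module. This step does not require the interviewer to have spoken to the participant before.

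**Step 3: who is revealed by the process interview?** It covers both DVD arms: 2 × 150 = 300 of 450 (67%) by planned allocation. Project Monitoring, item 4, adds that participants report non-receipt of the DVD to CSR interviewers. This knowledge reaches an outcome interview only if the same individual later makes the T2 or T3 call, or if it is passed on. The documents establish one staff pool. They do not say that the same person calls the same participant twice.

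**Step 4: which outcomes are exposed?**

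| Outcome | Source | Exposure |
|---|---|---|
| Screening completion | Medical record dates | Little; dates leave little room for judgement |
| Bowel-preparation rating | Nurse and endoscopist record | Not through interviewers; some judgement at abstraction |
| Anxiety, satisfaction, knowledge, beliefs at T2 | Interview | Yes, if asked after the navigator items |
| Anxiety, satisfaction at T3 | Interview | No arm-specific items in Table 3; only through earlier contact or disclosure by the participant |

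On bowel preparation, C.9 says the scale resembles Aronchick, that the term adequate may stand alone, and that use of the Boston scale is to be decided later. The abstractor may therefore have to interpret some entries.

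**Step 5: how large could a bias be?** The documents give no basis for a size. The following is an illustration only. Assume no true effect, 115 per group, and an interviewer-induced shift of b standard deviations in one arm. The standard error is √(2/115) = 0.132, and the two-sided rejection rate at 5% is Φ(b/0.132 − 1.96) + Φ(−b/0.132 − 1.96).
- b = 0.1: 12%
- b = 0.2: 33%
- b = 0.3: 62%

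The shift is an assumption throughout. H1.3 is also restricted to participants who complete colonoscopy, so fewer than 115 per group would contribute there and the rates would be lower.

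**The case against.** The strongest reply is that this is mostly a missing qualifier. C.7, in the design section, already limits the statement to what is feasible, and section J repeats it without the limit. That stands in part: the two copies need reconciling. But C.7 also credits blinding to the three-group design, so the qualifier does not supply a mechanism.

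A reader might go further and infer that the self-report outcomes are simply unblinded, or that interviewers know the arm of 300 participants when they collect outcomes. The documents do not support either reading. The order of questions within T2 is not given; if the navigator items already come last, the outcome answers are recorded before that module reveals anything. Carry-over from the process interview needs the same individual, or shared information, and neither is stated.

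Three further points stand. Interviews are structured and computer-assisted, interviewers are trained to full compliance, and 10% of calls are monitored; this limits interviewer influence, though it does not hide the arm. Participants' knowledge of their own arm is inherent in a trial of this kind and is a separate source of expectation effects, which question order cannot remove. And it would be too strong to say that the screening outcome is compromised, because it rests on recorded test dates extracted for all participants, including those who drop out.

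**Conclusion.** The concern holds in a limited form. Section J claims a property that the design does not have, and C.7 and J disagree on how firmly it is claimed. The T2 navigator items reveal the DVD+PN arm to the interviewer in about 115 calls (150 randomised). Exposure through the process interview is possible but not established.

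The outcomes at risk are the T2 self-report measures. How far they are affected depends on a question order that the documents do not give. The screening outcome is little affected, and T3 has no arm-specific items. The size and direction of any bias cannot be derived. This is a minor point and does not threaten the main comparison.

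**What to change.** 1. Reconcile C.7 and section J. Both should say that blinding of telephone interviewers is attempted but not assured, and how it is attempted. Remove the attribution to the three-group design.
2. In the T2 script, ask the navigator items after all outcome and belief items. If that is already the order, state it.
3. Abstract screening dates and bowel-preparation ratings with the arm hidden, and say who abstracts. The REDCap user-rights restrictions described under Data Integrity and Security could serve for this.
4. Report interviewer-collected outcomes as not assured to be blinded. Reordering cannot undo earlier contact or disclosure by participants, so this is needed in addition to item 2.

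The cost is text, a question-order setting and an access setting. There are two caveats. Six-month follow-up was already under way by 31 May 2019, so a change in order would give earlier and later participants different sequences; the date of any change should be recorded and noted in the report. Also, research assistants' check-in calls include a DVD-player check for the DVD arms (C.8). If those assistants also abstract records, hiding the field will not blind them for participants they have called.

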#### A. Research Staff Training

Three groups of research staff will be trained and monitored throughout the project.

- 1) Research Assistants (RAs) working on-site at the Indiana University School of Nursing will be trained to effectively recruit participants by mail and phone. These RAs will be specially trained in the recruitment of minority and low-income patients. Training will focus on: 1) HIPAA and IRB regulations designed to protect research participants; 2) mailing of recruitment materials and follow-up recruitment by phone using standardized scripts to explain the study and answer questions; 3) eligibility assessment; 4) obtaining both verbal informed consent and verbal HIPAA Authorization to participate; 5) scheduling the T1 (baseline) interview; 6) handling problems or questions that arise during phone recruitment; 7) use of the REDCap tracking database to log recruitment procedures; and 8) study procedures for on-going recruitment monitoring and quality assurance. Recruiters will practice and role-play phone recruitment until they have reached 100% compliance with guidelines for recruitment.
- 2) The second group of research staff includes experienced interviewers/data collectors employed by the Center for Survey Research (CSR) at Indiana University. Prior to the study-specific training described below, CSR interviewers/data collectors will have completed a rigorous 9-hour telephone interviewing training course, with four hours spent in hands-on practical experience in which the trainee-to-supervisor ratio is 5:1. This training course covers: 1) the interviewer's role in survey research; 2) standardized interviewing techniques; 3) administration of survey introductions and refusal aversion techniques; 4) use of computerized sample management and data collection systems; 5) protection of human subjects and sensitive information; and 6) daily case management. Comprehension of concepts and techniques and skill in their execution are assessed through a battery of tests at appropriate intervals in the training course; trainees do not matriculate to the next phase until all prior phases are mastered. CSR interviewers/data collectors will then be trained on: 1) administering the study's four phone interviews: T1 (baseline), DVD Process, T2 (6 month) and T3 (9 month); 2) handling problems or questions that arise during data collection; 3) recognizing and reporting potential adverse events; and 4) data monitoring and quality assurance procedures. Training will include demonstrations of effective data collection interviews using the computer-assisted telephone interview software (CATI). Following demonstrations and practice sessions, interviewers/data collectors will role-play and receive feedback until they have reached 100% compliance with guidelines for interviewer data collection integrity.
- 3) The third group of research staff includes our School of Nursing research nurse employees who will serve as patient navigators to deliver the navigation intervention by phone. Initial training will be conducted during two separate sessions with the first being a full, one-day session. This first day of training will consist of a series of presentations by our Ohio State University co-investigators, [name] and [name], who are experts in navigation. Training objectives will be to have navigators understand the scope of their role, provide them with support, as well as guide them to resources to assist participants with financial and transportation issues. The REDCap database for documenting navigation encounters will also be introduced. A second half-day

session will be scheduled when the REDCap navigation database is finished so that a live demonstration can be provided to the nurses. This second session will also include a presentation on intervention fidelity and quality assurance by an Ohio State quality assessor. The DVD intervention will be presented so that navigators know exactly what colon health information participants will receive prior to their contacting them. Navigators will be refreshed on their responsibilities and will practice and role-play until they have reached 100% compliance with the navigation intervention protocol. Prior to navigating their first participant, the study's Project Manager will meet with each navigator. The purpose of this final, pre-navigation session is to confirm that: 1) there are no issues with accessing and utilizing the REDCap navigation database; 2) the audio recorder works properly with the phone set-up, and 3) the navigator is able to deliver the intervention content effectively in a simulated call.

